6.3. Screen Failures

Individuals who do not meet the criteria for participation in this study (screen failure) for reasons other than not meeting amyloid burden criteria may be re-screened. Individuals may be re-screened once. The interval between an initial screen and a re-screen should be at least 8 weeks. When rescreening is performed the participants must sign a new informed consent form (ICF) and will be assigned a new identification number. Approval from the sponsor must be obtained in advance for all re-screens.

6.4. Lifestyle and/or Dietary Requirements

Study participants should be instructed not to donate blood or blood products during the study or for 8 weeks following the study.

Males who undergo PET scans during the study must be instructed not to donate sperm for 24 hours after each scan, and if they have female partners of child-bearing potential, to abstain from sex for 24 hours after each scan.

7. Treatment

7.1. Treatments Administered

This study involves a comparison of solanezumab 400 mg versus placebo administered intravenously every 4 weeks. The investigator or his/her designee is responsible for the following:

- explaining the correct use of the investigational agent to site personnel
- verifying that instructions are followed properly
- maintaining accurate records of investigational product dispensing and collection
- at the end of the study returning all unused medication to Lilly, or its designee, unless the sponsor and sites have agreed all unused medication is to be destroyed by the site, as allowed by local law

7.2. Method of Treatment Assignment

Patients who meet all criteria for enrollment will be randomized to double-blind treatment at Visit 2. Assignment to treatment groups will be determined by a computer-generated random sequence using an interactive web-response system (IWRS). The IWRS will be used to assign a vial containing double-blind investigational product to each patient. Site personnel will confirm that they have located the correct vial by entering a confirmation number found on the vial into the IWRS.

To achieve between-group comparability, the randomization will be stratified by site and by use of florbetapir PET scanning or CSF for study eligibility.

7.2.1. Selection and Timing of Doses

Infusion should occur over the course of at least 30 minutes. Premedication for dosing is not planned; however, if a patient demonstrates an infusion reaction to the study drug suggestive of allergy or hypersensitivity, the patient may be premedicated at the discretion of the investigator with appropriate medications (for example, diphenhydramine hydrochloride and/or acetaminophen), and the infusion time may be extended for the remaining infusions. An attempt should be made to complete the infusion within 2 hours of when first started. Patients should be observed for approximately 1 hour following the first infusion of study drug at Visit 2. Any premedications given are to be documented as concomitant therapy. The actual time of all dose administrations will be recorded in the patient's case report form (CRF).

Note that all cognitive and functional scales are to be administered before infusions.

7.3. Blinding

This is a double-blind study. To preserve the blinding of the study, a minimal number of Lilly personnel will see the randomization table and treatment assignments before the study is complete.

Emergency unblinding for AEs may be performed through the IWRS, which may supplement or take the place of emergency codes generated by a computer drug-labeling system. This option may be used ONLY if the patient's well-being requires knowledge of the patient's treatment assignment. All actions resulting in an unblinding event are recorded and reported by the IWRS.

If an investigator, site personnel performing assessments, or patient is unblinded, the patient must be discontinued from the study. In cases where there are ethical reasons to have the patient remain in the study, the investigator must obtain specific approval from a Lilly clinical research physician (CRP) for the patient to continue in the study.

In case of an emergency, the investigator has the sole responsibility for determining if unblinding of a patient's treatment assignment is warranted. Patient safety must always be the first consideration in making such a determination. If the investigator decides that unblinding is warranted, the investigator should make every effort to contact the Lilly CRP prior to unblinding a patient's treatment assignment. If a patient's treatment assignment is unblinded, Lilly must be notified immediately.

7.4. Packaging and Labeling

Clinical trial materials will be labeled according to the country's regulatory requirements.

7.5. Preparation/Handling/Storage

The site will be provided vials containing 400 mg/20 mL of solanezumab (or 20 mL placebo). The vials should be stored at 2°C to 8°C (36°F to 46°F).

For each dose, the content of 1 vial will be diluted with sterile sodium chloride intravenous infusion (0.9%) to a total volume of approximately 70 mL. Before infusion, the diluted solution should be inspected visually for particulate matter or discoloration. If particulate matter or discoloration is present, the solution should be discarded and a new solution made. After each intravenous bag is prepared, it will be identified as a dose of study drug without identification of the drug or dose. Once prepared, the infusion solution should be stored at room temperature (~25°C) for a total of no more than 6 hours.

7.6. Dose Modification

Not applicable.

7.7. Treatment Compliance

Because dosing occurs at study visits, patients who attend all visits and successfully receive infusions are automatically compliant with treatment. Any infusions at which 75% (approximately 52.5 mL when mixed in a 70-mL bag of normal saline) or more of the infusate is given will be considered a complete infusion.

If a patient attends a visit but does not receive a complete infusion (for example, due to technical complications), every effort should be made to complete the infusion within 24 hours if possible. If less than 75% of the infusion solution is given, this must be recorded as an incomplete infusion in the CRF.

Missed infusions should be recorded on the CRF. A patient will be considered significantly noncompliant if he or she misses 2 consecutive infusions, or 4 or more infusions at any time, and may be discontinued from the study. Patients who miss 2 consecutive infusions or 4 or more infusions for medical reasons (for example, MRI findings) can continue the study with approval of the sponsor.

7.8. Concomitant Therapy

For patients who are taking medications that may have an acute effect on cognition (and therefore on cognitive testing) and who must change doses or stop or start such medications, the sponsor or designee must be contacted beforehand to determine whether the patient should continue in the study and whether the clinical outcome measures should be performed. Starting on antimentia treatment is allowed during the trial for patients who worsen clinically during the study; however, the sponsor or designee must be contacted before initiation of therapy, and dosing should remain stable once a target dose is achieved. Sponsor approval must also be obtained for any subsequent dosing changes. A list of medications requiring sponsor consultation is provided in a separate manual of operations.

All concomitant medication taken during the study must be recorded on the Concomitant Medication CRF. Patients and their study partners will be instructed to consult the investigator or other appropriate study personnel at the site before initiation of any new medications or supplements and before changing dose of any current concomitant medications or supplements.

Patients who are receiving AChEIs and/or memantine are permitted to enter the study if stable on these medications prior to randomization.

Use of sedatives or hypnotics (including medications with sedating side effects such as antihistamines) should be avoided for 8 hours before administration of the cognitive and functional tests unless they are given chronically.

7.9. Treatment after Study Completion

The availability of an extension study will be determined before the first patient completes Visit 28. If an extension study is available, patients who complete Study LZBE may be eligible to participate if enrollment criteria for the extension study are met. Patients participating in such a study would receive study medication for the extension study only after all assessments for Study LZBE are completed. Patients not participating would not receive any study medication after the last infusion visit for Study LZBE (Week 100).

8. Discontinuation Criteria

8.1. Discontinuation of Inadvertently Enrolled Patients

If the sponsor or investigator identifies a patient who did not meet enrollment criteria and was inadvertently enrolled, a discussion must occur between the sponsor CRP and the investigator to determine if the patient may continue in the study. If both agree it is medically appropriate to continue, the investigator must obtain documented approval from the sponsor CRP to allow the inadvertently enrolled patient to continue in the study with or without treatment with investigational product.

8.2. Discontinuation from the Study

Patients will be discontinued from the study drug and from the study in the following circumstances, and will undergo early discontinuation procedures as shown in the Schedule of Activities (Section 2):

- Prolonged acute infusion reaction suggestive of allergic/hypersensitivity reaction (that is, not rapidly responsive to medication such as antihistamines, nonsteroidal anti-inflammatory drugs, and/or narcotics and/or brief interruption of infusion)

Note: Acute allergic/hypersensitivity reactions may occur with any agent that causes cytokine release (for example, monoclonal antibodies or other biological agents). Cytokine release may or may not be related to the mechanism of the infused biologic agent. Signs and symptoms usually develop during or shortly after drug infusion and generally resolve completely within 24 hours of infusion. Signs/symptoms may include: drug fever, arthralgia, bronchospasm, cough, dizziness, dyspnea, fatigue, headache, hypertension, hypotension, myalgia, nausea, pruritus, rash, rigors/chills, sweating (diaphoresis), tachycardia, urticaria, and vomiting.

- Requirement for a ferromagnetic implant or insertion of a cardiac pacemaker that is not MRI-compatible
- An investigator, site personnel performing assessments, or a patient is unblinded to a specific patient's treatment assignment.
- Enrollment in any other clinical trial involving an investigational product or enrollment in any other type of medical research judged not to be scientifically or medically compatible with this study
- Participation in the study needs to be stopped for medical, safety, regulatory, or other reasons consistent with applicable laws, regulations, and good clinical practice (GCP).
- Investigator decision: The investigator decides that the patient should be discontinued from the study. If the patient, for any reason, requires treatment with another therapeutic agent that has been demonstrated to be effective for treatment of the study indication, discontinuation from the study occurs prior to introduction of the new agent.

- Patient decision: The patient or the patient's designee requests to be withdrawn from the study.
- Adverse event: If the investigator decides that the patient should be withdrawn from the study because of an SAE or a clinically significant laboratory value, the investigational product is to be discontinued and appropriate measures are to be taken. Lilly or its designee is to be alerted immediately (Section 8.2).

In addition, patients *may* be discontinued from the study drug and from the study in the following circumstances, and if discontinued, will undergo early discontinuation procedures as shown in the Schedule of Activities (Section 2):

- Appearance of clinically significant new cerebral ischemic or hemorrhagic events or ARIA-E (amyloid-related imaging abnormality—edema/effusions, also known as cerebral vasogenic edema) by MRI (Section 9.3.6); patients with new MRI findings can continue to participate in the study depending on clinical significance as determined by the investigator.

Note: While most cases of ARIA-E are asymptomatic, when symptoms do occur they are reported to be most commonly headache, worsening of cognitive function, alteration of consciousness, seizures, unsteadiness, and vomiting. Even when symptomatic ARIA-E is present, in most cases treatment is not required beyond discontinuation of the study medication until the imaging abnormalities are resolved. If a patient simultaneously develops more than one of the symptoms suggestive of ARIA-E; that is, headache, worsening of cognitive function, alteration of consciousness, seizures, unsteadiness, or vomiting, then an unscheduled MRI may be obtained. A single symptom suggestive of ARIA-E of sufficient severity may also warrant an MRI. The unscheduled MRI should be performed in the same manner as the currently scheduled MRIs in the protocol, which includes sending the images for central review.

- Discontinuation of the investigational product for abnormal liver tests **should be considered** by the investigator when a patient meets one of the following conditions after consultation with the Lilly designated medical monitor:
 - ALT or AST >8X ULN
 - ALT or AST >5X ULN for more than 2 weeks
 - ALT or AST >3X ULN and total bilirubin level (TBL) >2X ULN or prothrombin time >1.5X ULN
 - ALT or AST >3X ULN with the appearance of fatigue, nausea, vomiting, right upper-quadrant pain or tenderness, fever, rash, and/or eosinophilia (>5%)
 - alkaline phosphatase (ALP) >3X ULN
 - ALP >2.5X ULN and TBL >2X ULN
 - ALP >2.5 ULN with the appearance of fatigue, nausea, vomiting, right quadrant pain or tenderness, fever, rash, and/or eosinophilia (>5%)

- Mean Bazett-corrected QT interval (QTcB) >500 msec and an absolute change >60 msec (or equivalent JTcB changes if appropriate) when compared with baseline (the most recent measurement made at either Visit 1 or Visit 2)
- Missed infusions: If a patient misses 2 consecutive infusions, or 4 or more infusions at any time overall during the study, the patient may be discontinued from the study. Patients who miss 2 consecutive infusions or 4 or more infusions for medical reasons (for example, MRI findings) may continue the study with approval of the sponsor.

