10.1. Determination of Sample Size

Power and sample size calculations have been based on the analysis of the primary objective using an effect size calculation of treatment difference at the end of the study.

To calculate power, we used an expected decline in ADAS-Cog₁₄ at 2 years of 4.41 points for placebo-treated patients and 3.21 points for solanezumab-treated patients, with a common standard deviation of 8 (Doraiswamy et al. 2014). This is equivalent to a difference of 1.2 points over 2 years, with an effect size = 0.15. Based on these assumptions and a 25% discontinuation rate, 1225 randomized patients per arm (919 completers per arm) or 2450 total randomized patients will have approximately 89% power to detect a significant treatment difference at 2 years using a 2-sided significance level of 0.05.

Patients who are randomized but not administered treatment may be replaced to ensure that enough patients may complete the study.

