10.2. General Statistical Considerations

Statistical analysis of this study will be the responsibility of Eli Lilly and Company or its designee.

All analyses will follow the intent-to-treat (ITT) principle unless otherwise specified. An ITT analysis is an analysis of data by the groups to which patients are assigned by random allocation, even if the patient does not take the assigned treatment, does not receive the correct treatment, or otherwise does not follow the protocol. When change from baseline is assessed, patients will be included in the analysis only if both a baseline and a postbaseline measure are available. Unless otherwise defined, a baseline measure is the last non-missing observation collected prior to the first infusion of study medication. Endpoint is the last non-missing postbaseline measurement.

For mixed-effect model repeated measure (MMRM) models, observations collected at nonscheduled visits will not be included in the analyses. For analyses using last observation carried forward, the last non-missing postbaseline observation (scheduled or unscheduled) will be used to calculate change from baseline.

Unless otherwise noted, all tests of treatment effects will be conducted at a 2-sided alpha level of 0.05; 2-sided confidence intervals (CIs) will be displayed with a 95% confidence level. All tests of interactions between treatment and other factors will be conducted at an alpha level of 0.05.

Any change to the data analysis methods described in the protocol will require an amendment ONLY if it changes a principal feature of the protocol. Any other change to the data analysis methods described in the protocol, and the justification for making the change, will be described in the CSR. Additional exploratory analyses of the data will be conducted as deemed appropriate.

Complete details of the statistical methods to be used in this study are contained in the statistical analysis plan (SAP).

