10.2.1. Analysis Populations

The primary and secondary efficacy measures will be analyzed using the ITT population. In addition, each of these measures will be analyzed using the per-protocol population and the completer population to verify the robustness of the results. Summaries and analyses for safety measures will be based on the safety population. Tabulation of the number and percentage of patients included in each population will be provided. The SAP contains detailed descriptions for each of these patient populations.

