10.4. Primary and Secondary Analyses

10.4.1. Primary Analyses

The primary objective of this study is to test the hypothesis that intravenous infusion of solanezumab will slow cognitive decline as compared with placebo in patients with prodromal AD. This will be assessed using an MMRM analysis of the ADAS-Cog₁₄ in patients with prodromal AD at baseline (Visit 1 MoCA score of 17 to 28), in which the specific hypothesis is that the cognitive decline from baseline at the end of the treatment period (104 weeks) for solanezumab will be significantly less than that for placebo.

The change from baseline score on the ADAS-Cog₁₄ at each scheduled postbaseline visit (according to the Study Schedule) during the treatment period will be the dependent variable. The model for the fixed effects will include terms for 7 effects: baseline score, pooled investigator, treatment, visit, treatment-by-visit interaction, concomitant AChEI and/or memantine use at baseline (yes/no), and age at baseline. Visit will be considered a categorical variable with values equal to the visit numbers at which the scales were assessed. The null hypothesis is that the contrast between the solanezumab-treated patients versus placebo-treated patients at the last visit equals zero. An unstructured covariance matrix will be used to model the within-patient variance-covariance errors. If the unstructured covariance structure matrix results in a lack of convergence, the following tests will be used in sequence: heterogeneous Toeplitz covariance structure, heterogeneous autoregressive covariance structure, heterogeneous compound symmetry covariance structure, and compound symmetry covariance structure.

The Kenward-Roger approximation will be used to estimate the denominator degrees of freedom.

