6.1. General Considerations

Statistical analysis of this study will be the responsibility of Eli Lilly and Company (hereafter Lilly).

On 10 January 2017, approximately 6 months after the first subject entered the LZBE study, the study was discontinued due to sponsor decision. After careful review of additional data analyses from the solanezumab Phase 3 EXPEDITION3 (H8A-MC-LZAX) study in subjects with mild dementia due to AD, Lilly did not find sufficient scientific evidence that solanezumab would likely demonstrate a meaningful benefit to subjects with prodromal AD as defined by the LZBE study protocol. The study was not stopped for safety reasons. Based on EXPEDITION3 results, there were no new safety signals identified.

The 26 randomized subjects in the study are to be discontinued from the double-blind treatment period at the early discontinuation visit and are requested to return to the follow-up visit (Visit 301) 4 months after the last dose according to the protocol. The study DBL will happen at the end of the trial after the last subject has completed the follow-up visit. A synopsis report with attachments will summarize the study results for the early discontinued study and this statistical analysis plan will pre-specify analyses for the study synopsis.

In general, no analyses will be conducted to address any primary, secondary, or exploratory efficacy objectives because sufficient data will not be available for reliable efficacy evaluation in this early discontinued study. Safety data will be listed or summarized. No statistical comparison of treatment effect will be conducted.

All analyses will follow the intent-to-treat (ITT) principle unless otherwise specified. An ITT analysis is an analysis of data by the groups to which subjects are assigned by random allocation, even if the subjectdoes not take the assigned treatment, does not receive the correct treatment, or otherwise does not follow the protocol. When change from baseline is assessed, subjects will be included in the analysis only if both a baseline and a postbaseline measure are available. Unless otherwise defined, a baseline measure is the last non-missing observation collected prior to the first infusion of study medication. Endpoint is the last non-missing postbaseline measurement.

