6.3. Analysis Populations

Table LZBE.6.1 below defines each of the analysis populations used in this study. Table LZBE.6.2 lists the study measures that will be summarized and/or analyzed in each population.

Table LZBE.6.1. Analysis Populations for Study H8A-MC-LZBE

Population Name	Description of Population
All Subjects Entered	All subjects who signed informed consent.
ITT Population	All randomized subjects.
Safety Population	All randomized subjects with at least 1 complete or partial infusion of study medication.

Abbreviation: ITT = intent-to treat.

Table LZBE.6.2. Study Measures Summarized for Each Analysis Population

Population Name	Variables Assessed
ITT Population	Tables and Listings of the following: subject disposition, subject characteristics, and concomitant medications
Safety Population	Tables and Listings of the following: adverse events, laboratory results, vital signs, MRI safety data, and suicidal ideation or behavior

Abbreviations: ITT = intent-to treat; MRI = magnetic resonance imaging.

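### Does the Week-104 primary analysis need a check on its missing-data assumption, and must compliance leave the baseline subgroup list?

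*Protocol*

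**What the plan says.** The primary analysis (Protocol 10.4.1) is a likelihood MMRM of change in ADAS-Cog14 with visit as a category: "The null hypothesis is that the contrast between the solanezumab-treated patients versus placebo-treated patients at the last visit equals zero". The last visit is Week 104.

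On stopping, Protocol 8.2 says: "Patients will be discontinued from the study drug and from the study in the following circumstances, and will undergo early discontinuation procedures". Sections 7.3, 7.7, 8.1 and 8.2 allow case-by-case exceptions. The Schedule of Activities places ADAS-Cog14 at eight postbaseline visits (V5, V8, V11, V15, V18, V21, V24, V28) and at early discontinuation, but not at follow-up Visit 301.

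On robustness, Protocol 10.2.1 says that "each of these measures will be analyzed using the per-protocol population and the completer population to verify the robustness of the results", and then that "The SAP contains detailed descriptions for each of these patient populations". Section 10.2 likewise leaves full method details to the SAP. Section 10.3.1 compares discontinuation between arms, by reason, with Fisher's exact test. Section 10.4.2.1 adds a slopes MMRM.

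On subgroups, Protocol 10.7.2 lists compliance with study drug among demographic and baseline characteristics. It leaves the groupings to the SAP and classes all subgroup analyses as secondary. Section 7.7 defines significant noncompliance by missed infusions.

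The SAP was approved after the sponsor stopped the trial. Its Section 6.1 says: "In general, no analyses will be conducted to address any primary, secondary, or exploratory efficacy objectives because sufficient data will not be available". It also rules out any statistical comparison of treatment effect. On populations, Section 6.3 says "Table LZBE.6.1 below defines each of the analysis populations used in this study", and the table holds three: All Subjects Entered, ITT and Safety.

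**The concern.** A patient who leaves early generally supplies no Week-104 score. The MMRM in effect predicts that score from the patient's earlier visits and from patients who stayed, which is valid only under missing-at-random. Neither document states this assumption or names an analysis that varies it.

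The two analyses offered as robustness checks do not fill the gap. Completers are chosen by an event after randomization, and neither restricted set adds information on the missing values. If solanezumab leavers did worse than predicted, the completer result would not move, and its agreement with the MMRM could be mistaken for reassurance. The slopes MMRM also rests on missing-at-random.

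The compliance entry looks like a plain misclassification. Compliance is known only after treatment begins, so a contrast within compliance levels is not a randomized comparison. It does not belong beside sex, age or APOE4 status.

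In a completed trial of 2450, the credibility of a modest positive result would be at stake.

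**Working it through.** **Inputs.** Protocol 10.1: 2-year decline of 4.41 (placebo) and 3.21 (solanezumab), SD 8, two-sided alpha 0.05, 25% discontinuation, 1225 randomized and 919 completers per arm, stated power about 89%. It adds: "This is equivalent to a difference of 1.2 points over 2 years, with an effect size = 0.15". Synopsis: 2450 randomized, 1838 completed, so 2450 − 1838 = 612 leavers.

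**The plan's own figure.**
- SE = 8 × √(2/919) = 0.373.
- Smallest significant difference = 1.96 × 0.373 = 0.731.
- Power at 1.2 = Φ(1.2/0.373 − 1.96) = 0.895.

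The stated 89% reproduces.

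**What the completer analysis can detect.** Let D be the observed difference (placebo minus solanezumab). Suppose placebo leavers behave as missing-at-random predicts and solanezumab leavers average δ points worse. The difference over all randomized patients is then D − 0.25δ. At D = 1.2:

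| δ | All-randomized difference | p (SE 0.373) | Completer difference |
|---|---|---|---|
| 0 | 1.20 | 0.001 | 1.20 |
| 1 | 0.95 | 0.011 | 1.20 |
| 1.87 | 0.73 | 0.050 | 1.20 |
| 3 | 0.45 | 0.23 | 1.20 |
| 4.8 | 0.00 | 1.0 | 1.20 |

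The completer column is constant because leavers do not enter it. A large simulation agreed. It assumed about 24% dropout depending on the last observed score, plus extra worsening after dropout of 0, 1.2, 2 or 4.8 points on solanezumab. The true difference fell from 1.20 to 0.92, 0.73 and 0.07, while the missing-at-random and completer estimates both stayed near 1.20.

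**How large a departure matters.** Significance is lost at δ = (D − 1.96 × SE)/0.25. With the completers-only SE:
- D = 0.8: (0.8 − 0.731)/0.25 = 0.27
- D = 1.0: (1.0 − 0.731)/0.25 = 1.07
- D = 1.2: (1.2 − 0.731)/0.25 = 1.87
- D = 1.5: (1.5 − 0.731)/0.25 = 3.07

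These shifts are too small for the planned model, because the MMRM also uses leavers' scores from before they left. Assume 25% dropout spread evenly over the eight visits, SD rising to 8, and a constant within-patient correlation of 0.5 to 0.85. The SE is then 0.357 to 0.338, and:
- at D = 1.2, δ = (1.2 − 1.96 × 0.357)/0.25 = 2.00, rising to 2.15;
- at D = 0.8, δ = 0.40 to 0.55.

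With all 1225 per arm observed, SE = 8 × √(2/1225) = 0.323, which caps δ at 2.27 and 0.67. Against the planned placebo decline, 1.87/4.41 = 42%, so a result at the planned effect tolerates a substantial departure. A result barely over the threshold does not, but almost any perturbation would overturn it.

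**Compliance.** Protocol 7.7 counts infusions missed during treatment, and 10.3.5 uses that definition for a between-arm comparison. Section 10.7.2 gives no baseline version of the variable. The label is therefore wrong on any reading, although the grouping itself was left to the SAP.

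**What the trial will compute.** SAP 6.1 gives 26 randomized patients, no analysis addressing efficacy objectives and no treatment comparison. Neither the Week-104 MMRM nor the completer, per-protocol and subgroup analyses will be run.

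**The case for a change.** The strongest case for a change treats the protocol as a plan in its own right. It names checks said to verify robustness that cannot do so for a quarter of the sample, and it calls a post-randomization variable baseline. A tipping-point analysis would need no new visits and only modest programming, and the compliance entry needs only a wording edit. All of that is accurate as a description of the protocol text.

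Several points weaken it as a call to act. Section 10.2.1 does not say that the completer and per-protocol analyses test missing-at-random; reading it so is an inference. The by-reason comparison of discontinuation in 10.3.1 does not test missing-at-random either, but it would show differential dropout. Eight scheduled assessments give the MMRM real information on leavers. Naming a particular sensitivity method is the kind of detail Section 10.2 left to the SAP. A SAP written after termination cannot show what a full one would have held, so its silence is not evidence of an omission.

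The ITT entry in Appendix 1, which speaks of following patients regardless of compliance, sits awkwardly beside Section 8.2. It is a glossary statement of principle, and the working ITT rule in 10.2 is not contradicted.

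What stands is the limit of the completer check and the misplaced compliance label. Neither bears on any analysis that will be done.

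**Conclusion.** No change to the plan. As a reading of the protocol the concern is right: the Week-104 contrast rests on missing-at-random for about 612 planned leavers, the named checks cannot probe that assumption, and compliance is not a baseline characteristic. But nothing would be gained by correcting it here. With 26 patients randomized and every efficacy analysis and treatment comparison cancelled, no estimate, p-value or conclusion depends on either point. The missing sensitivity analysis is also a detail that the protocol handed to the SAP, and the compliance label is a slip in a list of secondary analyses.

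On size, had the trial run to plan and observed 1.2 points, the departure needed to lose significance is about 1.9 points with the completers-only SE, and about 2.0 to 2.15 with an MMRM SE. These figures assume 25% dropout, SD 8, a shift in solanezumab leavers only and, for the second range, evenly spread dropout with within-patient correlation of 0.5 to 0.85. They are illustrations, not estimates of bias. No size of bias is claimed for the compliance subgroup.
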